### 8.5.2 Study Stopping Rule

If any subject experiences a life-threatening AE (Grade 4) that is considered to be related to study drug, any further dosing in all enrolled subjects will be suspended until the Sponsor Medical Team has evaluated the event and determined the next appropriate course of action. At any time during the study, the study may be discontinued if the Sponsor Medical Team determines that further drug exposure would pose an undue risk to subjects.

### 8.5.3 Individual Stopping Rule

Dosing for any individual subject will be discontinued (ie, further treatment with the study drug will not be given) if the subject experiences any study drug-related SAE or any study drug-related non-serious AE that, in the judgement of the Investigator (following consultation with Medical Monitor, if desired) suggests that it could be unsafe to administer further study drug to that subject.

Subjects who withdraw from this study due to an AE determined to be related to study drug are to be followed until there is:

- Resolution or stabilization of the AE determined to be related
- The subject is lost to follow-up
- The event is otherwise explained

If there is a persistent AE contributing to discontinuation that is determined to be related to SYNT001, subjects must be followed with appropriate medical management until resolution or stabilization.

Additionally, a subject will be discontinued from further treatment with study drug, at the discretion of the Investigator with consultation with the Medical Monitor, if they require a significant increase in doses of anti-WAIHA medications for the management of WAIHA.

If dosing with study drug is stopped because of an AE/SAE, or because of significant increase in doses of anti-WAIHA medications, or any other reason for prematurely discontinuation of study drug during the treatment period, the subject should be encouraged to attend, at a minimum, the ET visit (Day 112 for Cohort 1 or Day 91 for Cohort 2). Subjects in Cohort 2 will also be encouraged to attend the remaining follow up visits on Days 112, and 140.

## 9. STUDY DRUG

For detailed information regarding SYNT001 preparation and administration, refer to the Pharmacy Manual.

### 9.1 SYNT001

SYNT001 is provided in vials containing 5 mL SYNT001 (extractable volume) at a nominal concentration of 50 mg/mL. The product is supplied as a liquid at pH  $6.5 \pm 0.5$ . SYNT001 is diluted in dextrose 5% in water (D5W) to prepare the solution for infusion. SYNT001 will be infused via IV in 250 mL over 1 hour  $\pm 15$  minutes using a 0.2-micron, inline filter.

Investigators may adjust the duration of the infusion if needed to increase tolerability. Prepared SYNT001 should be used within 4 hours as described in the pharmacy manual. For detailed information regarding SYNT001 preparation and administration, refer to the Pharmacy Manual.

### 9.2 Dose Requirements

The specification for host cell deoxyribonucleic acid (DNA) in SYNT001 is  $< 2$  pg/mg, the limit of quantitation of the assay. To comply with regulatory guidelines, which specify a maximum level of 10 ng host cell DNA per dose, dosing per subject is limited to 5000 mg SYNT001. For example, a subject with a body weight of 166 kg and enrolled in the  $\leq 30$  mg/kg dose cohort will receive  $\leq 4960$  mg SYNT001 per dose. If a subject's body weight extrapolates to an expected dose  $\geq 5000$  mg SYNT001, the dose will be capped to ensure the 5000 mg SYNT001 per dose limit is not exceeded.

### 9.3 Cohort Dosing

Enrolled subjects will receive SYNT001 according to their dose-cohort assignment:

**Cohort 1:** 10 mg/kg weekly x 5 doses

**Cohort 2:** 10, 20 or 30 mg/kg weekly x 3 doses (Loading), followed by 10, 20 or 30 mg/kg every other week x 5 doses (Maintenance). The Maintenance dose frequency may be increased to weekly (Cohort 2 alternative weekly maintenance schedule).

Up to 8 subjects may be enrolled in Cohort 1. After 4 subjects reach Day 42, the Sponsor Medical Team will review available safety and PD data and will decide the dosing regimen for Cohort 2.

### 9.4 Handling and Storage of SYNT001

SYNT001 will be supplied by the Sponsor and must be stored refrigerated ( $2^{\circ}\text{C}$  to  $8^{\circ}\text{C}/36^{\circ}\text{F}$  to  $46^{\circ}\text{F}$ ) in the carton and protected from light, in a securely locked area, accessible to authorized persons only, until needed for dose preparation.

## 9.5 Study Drug Accountability

The Investigator (or designee) is responsible for maintaining accurate accountability records of the study drug throughout the clinical study. Qualified site personnel will inventory the investigational product received and will maintain records of disposition of the drug, including dates, quantity and use. All study drug received at the site must be accounted for on an accountability log provided by the Sponsor. All dispensing and accountability records will be available for Sponsor review. Study drug accountability will be verified during on-site monitoring visits.

Upon the completion or termination of the study, and upon written authorization from the Sponsor, or its representative, all unused and/or partially used study drug should be returned or destroyed at the investigational site, as specified by Sponsor. It is the Investigator's responsibility to ensure that the Sponsor, or its representative, has provided written authorization that procedures for proper disposal of the study drug have been established, and that appropriate records of the disposal are documented and maintained. No unused study drug may be disposed of until fully accounted for by the Sponsor monitor (or designee).

## 9.6 Warnings and Precautions

**Note:** Subjects must not receive any vaccinations from within 2 weeks of screening until 28 days after the final dose of study drug.

### 9.6.1 Infusion-Related Reaction

SYNT001 will be administered as an IV infusion over 1 hour  $\pm$ 15 minutes. Investigators may adjust the duration of the infusion if needed to increase tolerability. As with all mAbs administered by IV infusion, IRR are possible. In nonclinical testing of SYNT001 in NHPs, clinical observations were limited to IRRs due to the immunogenicity of SYNT001 in NHPs. These reactions included transient emesis/vomitus which typically occurred within one hour of dosing at all dose groups, but only after the third weekly infusion following the development of ADAs. Transient histamine-type responses were noted 30 minutes post-dose in some animals in all dose groups, but only following the third weekly infusion as above. These reactions were consistent with a histamine reaction (decreased activity, periocular swelling, erythema, facial flushing, eyelids partially/completely closed, and/or generalized weakness). With the exception of vomitus/emesis and red skin discoloration associated with injection or blood draw sites, these observations spontaneously resolved within 1-hour post-dose. Subsequent pretreatment with intramuscular diphenhydramine prevented further histamine-type reactions. All doses of SYNT001 were administered by bolus infusion over approximately 5 minutes in the NHP studies. Since xenobiotic hypersensitivity reactions commonly occur in NHPs following administration of humanized proteins, neither infusion reactions nor ADAs are considered predictive of immunogenicity or toxicity in humans ([Bugelski and Treacy, 2004](#); [ICH S6\(R1\), 2011](#); [Ponce et al., 2009](#)).

In general, infusion reactions to monoclonal antibodies observed in human studies typically develop within 30 minutes to 2 hours after the initiation of drug infusion, although symptoms

[figure not shown]
may be delayed for up to 24 hours. Most are mild in severity, although severe and even fatal reactions can occur.

### **9.6.2 Guidelines for Grading and Management of Allergic or Infusion-Related Reactions**

[figure not shown]
Allergic and/or infusion-related reactions include hypersensitivity reactions and cytokine release syndromes. These reactions are experienced by patients during or within hours of the infusion of monoclonal antibody therapy. Symptoms can include flushing, alterations in heart rate and blood pressure, dyspnea, bronchospasm, back pain, fever, urticaria, edema, nausea, and all types of rashes. Anaphylaxis is recognized as a severe, life-threatening, generalized, or systemic reaction. This is a medical emergency characterized by rapidly developing life-threatening airway and/or breathing and/or circulation problems usually associated with skin or mucosal changes.

Management of Grade 1 infusion reactions include interrupting the infusion or decreasing the rate of infusion by 50% and observing. Symptoms may also be treated as needed with medications such as diphenhydramine, hydrocortisone or acetaminophen, either alone or in combination, depending on the subject's signs and symptoms. If the infusion is interrupted or the infusion rate is decreased, it is important to note that all study drug infusions must be completed within 4 hours of SYNT001 administration. Management of Grade 2 and higher infusion reactions should include stopping the infusion of study drug. See [Figure 2](#) and [Figure 3](#) for details on the management of Grade 2 and Grade 3 infusion reactions. The severity of and management of allergic or infusion-related reactions will be graded and managed using NCI CTCAE Version 4.03 (see [Table 8](#)).

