### 3. STUDY OBJECTIVES AND ENDPOINTS

Primary Objective	Primary Endpoint
Safety: To evaluate the safety and tolerability of IV infusions of SYNT001 at different dose levels and dosing regimens in subjects with WAIHA	Safety: The evaluation of SYNT001 safety based on vital signs, physical examinations, electrocardiograms (ECGs), clinical safety laboratory tests, the incidence of AEs, treatment-emergent adverse events (TEAEs), and SAEs summarized by dose and dosing regimen, severity, and relationship to study drug
Secondary Objective	Secondary Endpoint
To evaluate the efficacy of doses of SYNT001 at different dose levels and dosing regimens on PD biomarkers	The evaluation of PD biomarkers based on absolute serum levels and percent change from baseline of total IgG, IgG subtypes (IgG1-4), immunoglobulin A (IgA), immunoglobulin M (IgM), albumin, and CIC summarized by dose, dosing regimen and time point
To determine the PK of SYNT001 following IV infusions at different dose levels and dosing regimens	The determination of PK parameters including half-life ( $t_{1/2}$ ), maximum serum concentration determined directly from the concentration-time profile ( $C_{max}$ ), observed time of peak serum concentration ( $T_{max}$ ), area under the serum concentration-time curve from pre-dose ( $time_0$ ) to 24 hours post-dose ( $AUC_{0-24}$ ), and area under the serum concentration-time curve from pre-dose ( $time_0$ ) to infinity ( $AUC_{0-\infty}$ ), (Cohort 1); maximum serum concentration determined directly from the maximum serum concentration and corresponding $T_{max}$ (Cohort 2) summarized by dose, dosing regimen and time point
To assess the efficacy of doses of SYNT001 at different dose levels and dosing regimens on disease markers	The assessment of WAIHA disease activity by absolute changes in the disease activity markers of hematocrit, hemoglobin, platelet count, reticulocyte count, lactate dehydrogenase (LDH), haptoglobin, and total and indirect bilirubin will be summarized by dose, dosing regimen and time point The direct Coombs test result (positive or negative) will be summarized by dose, dosing regimen and time point
To measure the immunogenicity of SYNT001 administered at different dose levels and dosing regimens	The immunogenicity of SYNT001, as determined by presence of anti-SYNT001 binding antibodies and neutralizing antibodies, summarized by dose, dosing regimen and time point

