**Figure 2. Management of Moderate (Grade 2) Infusion Reactions**

**Figure 3. Management of Severe (Grade 3 or Higher) Infusion Reactions**

**Table 8. Grading and Management of Allergic or Infusion-Related Reactions**

Adverse Event	Grade				
	1	2	3	4	5
Infusion-related reaction	Mild transient reaction; infusion interruption not indicated; intervention not indicated	Therapy or infusion interruption indicated but responds promptly to symptomatic treatment (eg, antihistamines, non-steroidal anti-inflammatory drugs [NSAIDS], narcotics, IV fluids): prophylactic medications indicated for ≤24 hours	Prolonged (eg, not rapidly responsive to symptomatic medication and/or brief interruption of infusion); recurrence of symptoms following initial improvement, hospitalization indicated for clinical sequelae	Life-threatening consequences; urgent intervention required	Death
Allergic reaction	Transient flushing or rash, drug fever <38.0°C. Intervention not indicated	Therapy or infusion interruption indicated but responds promptly to symptomatic treatment (eg, antihistamines, NSAIDS, narcotics, IV fluids): prophylactic medications indicated for ≤24 hours	Prolonged (eg, not rapidly responsive to symptomatic medication and/or brief interruption of infusion); recurrence of symptoms following initial improvement, hospitalization indicated for clinical sequelae (eg, renal impairment, pulmonary infiltrates)	Life-threatening consequences; urgent intervention required	Death
Anaphylaxis	–	–	Symptomatic bronchospasm, with or without urticarial; parenteral intervention indicated; allergy-related edema/angioedema; hypotension	Life-threatening consequences; urgent intervention required	Death
Cytokine release syndrome	Mild reaction; infusion interruption not indicated; intervention not indicated	Therapy or infusion interruption indicated but responds promptly to symptomatic treatment (eg, antihistamines, NSAIDS, narcotics, IV fluids): prophylactic medications indicated for ≤24 hours	Prolonged (eg, not rapidly responsive to symptomatic medication and/or brief interruption of infusion); recurrence of symptoms following initial improvement, hospitalization indicated for clinical sequelae (eg, renal impairment, pulmonary infiltrates)	Life-threatening consequences; pressor or ventilator support indicated	Death

Abstracted from NCI CTCAE Version 4.03.

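### Protocol 9.6.2 lists pausing and as-needed medication as Grade 1 management, but Table 8 defines Grade 1 by these not being indicated, so a Grade 2 infusion reaction can be recorded as Grade 1 (minor effect)

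*Protocol*

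**What the plan says.** Protocol 9.6.2 gives this for mild reactions: "Management of Grade 1 infusion reactions include interrupting the infusion or decreasing the rate of infusion by 50% and observing". The next sentence adds: "Symptoms may also be treated as needed with medications such as diphenhydramine, hydrocortisone or acetaminophen, either alone or in combination". Only after that does the paragraph turn to Grade 2 and higher, where management should include stopping the infusion, with Figures 2 and 3 for details.

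The paragraph closes by naming one standard for both purposes: "The severity of and management of allergic or infusion-related reactions will be graded and managed using NCI CTCAE Version 4.03", with a pointer to Table 8. The Grade 1 cells of Table 8 read:

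- Infusion-related reaction: "Mild transient reaction; infusion interruption not indicated; intervention not indicated"
- Cytokine release syndrome: "Mild reaction; infusion interruption not indicated; intervention not indicated"
- Allergic reaction: "Transient flushing or rash, drug fever <38.0°C. Intervention not indicated"

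Grade 2 in all three rows begins: "Therapy or infusion interruption indicated but responds promptly to symptomatic treatment". Anaphylaxis has no Grade 1 or Grade 2 entry.

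Severity is part of the primary endpoint. Protocol Section 3 has AEs, TEAEs and "SAEs summarized by dose and dosing regimen, severity, and relationship to study drug".

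**The concern.** The actions that 9.6.2 attaches to Grade 1 are the ones that Table 8 uses to separate Grade 1 from Grade 2. An investigator who pauses an infusion, gives an antihistamine and sees the symptoms settle has followed the Grade 1 instruction and may enter Grade 1. Read against Table 8, the same event is Grade 2 if the pause or the drug was indicated.

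Two things are at stake. One is the Grade 1/Grade 2 split in the severity tables that serve the primary endpoint. With about 15 sites and at most 20 subjects, or 20/15 ≈ 1.3 subjects per site, different site habits need not average out. The other is bedside conduct, because 9.6.2 pairs Grade 1 with pausing or slowing and Grade 2 with stopping.

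**Working it through.** The plan states no figure to reproduce. The check is a comparison of texts, then a look at where the grade is used.

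**Step 1: each action that 9.6.2 lists for Grade 1, against the Grade 1 cells of Table 8.**

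| Table 8 row | Pause | As-needed medication | 50% rate cut |
|---|---|---|---|
| Infusion-related reaction | conflict | conflict | not mentioned, no conflict |
| Cytokine release syndrome | conflict | conflict | not mentioned, no conflict |
| Allergic reaction | Grade 1 cell silent | conflict | not mentioned, no conflict |
| Anaphylaxis | no Grade 1 | no Grade 1 | no Grade 1 |

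**Step 2: does another text reconcile them?** Protocol 6.9, 10.1 and 10.3.6 and SAP 4.7.1 all name CTCAE 4.03 as the scale. None says how to grade a reaction that was paused or medicated as 9.6.2 permits. Figures 2 and 3 are not visible in the copy reviewed. By their titles they cover Grade 2 and Grade 3 or higher, so they are unlikely to define Grade 1.

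**Step 3: where the Grade 1/Grade 2 boundary is used.**

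- SAP 4.7.1 reports the worst grade of TEAEs and of drug-related TEAEs, and tabulates TEAEs by preferred term and grade. These can shift. So can the separate infusion-reaction summary, if it is shown by grade.
- Protocol 8.5.1 defines dose-limiting toxicity from Grade 3 events in at least 2 subjects, and 8.5.2 suspends dosing on a related Grade 4 event. Neither can shift.
- Protocol 8.5.3, the individual rule, turns on relatedness, seriousness and judgment. It sets no threshold at Grade 2.
- Incidence of any TEAE, and of Grade 3 or higher, cannot shift.

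**Step 4: size per re-graded subject.** The change in Grade 2 incidence is 1/n. At full enrolment:

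- Cohort 1: 1/8 = 12.5 percentage points
- Cohort 2: 1/12 = 8.3 points
- Total: 1/20 = 5.0 points

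In the overall worst-grade row a subject moves only if no other event already puts that subject at Grade 2 or above.

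**Step 5: how many subjects?** The documents give no rate of paused or medicated mild reactions, so no expected count can be derived. Protocol 2.2 reports that all 5 volunteers given 30 mg/kg had only Grade 1 AEs, and that 0 of 5 needed intervention. Those were single doses. Here subjects receive 5 doses in Cohort 1, and 3 + 5 = 8 or 3 + 10 = 13 in Cohort 2.

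**The case against.** The strongest reply is that the grading rule is already fixed. CTCAE 4.03 is named throughout, and the Grade 1 sentence in 9.6.2 starts from an assigned grade and says what may be done. It is not a grading criterion. Table 8 also turns on what is indicated, and a cautious pause may be done without being indicated. Finally, the plan shows the actions themselves whatever grade is entered. SAP 4.7.1 has rows for TEAEs, and drug-related TEAEs, leading to study drug interruption. SAP 4.5 summarizes medication for potential infusion reactions by cohort. Treatment given, action taken and infusion time are also recorded, listed or summarized.

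Most of this stands, and it is why the effect is small. It does not remove the conflict. The paragraph names Table 8 for management as well as grading, so the Grade 1 instruction cannot be set aside as a separate management rule. Interruption listed as the management of a grade reads as indicated, and so does a drug given as needed. The distinction between indicated and merely done is sensible, but no visible text states it.

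A reader might infer that every paused or medicated mild reaction will be misgraded. The documents do not support that: a pause that was not indicated remains Grade 1 under Table 8.

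**Conclusion.** The two texts contradict each other as written, and the consequence is minor. A mild reaction managed under 9.6.2 can be entered as Grade 1 when Table 8 makes it Grade 2, and the same ambiguity blurs whether the infusion is paused or stopped. The statistical effect is confined to the Grade 1/Grade 2 split in descriptive tables, at 12.5, 8.3 or 5.0 percentage points per re-graded subject. These figures assume full enrolment and, for the overall worst-grade row, no other event of Grade 2 or higher in that subject. They are not a forecast, because the number of such subjects is unknown.

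A reader might go further and infer that the primary safety endpoint is unreliable or that dose decisions could be distorted. The documents do not support this. No dose-limiting toxicity or stopping rule uses the Grade 1/Grade 2 boundary, SAP 4.7 makes all safety analysis descriptive, and interruptions and reaction medication are summarized independently of grade.

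**What to change.** Change Protocol 9.6.2 in four places:

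1. State that the grade is assigned from Table 8 alone, by what is clinically indicated and not by the action taken, so that a reaction for which interruption or medication is indicated is at least Grade 2.
2. Reword the Grade 1 sentence so that such reactions may be managed by observation, by slowing the rate by 50%, or by a precautionary pause, which does not by itself change the grade.
3. Move the as-needed medication sentence to Grade 2 management. If it stays under Grade 1, the medication half of the conflict remains.
4. Check the Grade 2 instruction to stop the infusion against Figure 2, so that regrading does not unintentionally force discontinuation for a mild reaction that resolves promptly.

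The cost is a few sentences and one figure check. Because the wording bears on treatment, it is a protocol modification that goes to the IRB under Section 14. It needs no new data, visits, tables or analyses, and no SAP change.

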**Figure 2. Management of Moderate (Grade 2) Infusion Reactions**

**Figure 3. Management of Severe (Grade 3 or Higher) Infusion Reactions**

**Table 8. Grading and Management of Allergic or Infusion-Related Reactions**

Adverse Event	Grade				
	1	2	3	4	5
Infusion-related reaction	Mild transient reaction; infusion interruption not indicated; intervention not indicated	Therapy or infusion interruption indicated but responds promptly to symptomatic treatment (eg, antihistamines, non-steroidal anti-inflammatory drugs [NSAIDS], narcotics, IV fluids): prophylactic medications indicated for ≤24 hours	Prolonged (eg, not rapidly responsive to symptomatic medication and/or brief interruption of infusion); recurrence of symptoms following initial improvement, hospitalization indicated for clinical sequelae	Life-threatening consequences; urgent intervention required	Death
Allergic reaction	Transient flushing or rash, drug fever <38.0°C. Intervention not indicated	Therapy or infusion interruption indicated but responds promptly to symptomatic treatment (eg, antihistamines, NSAIDS, narcotics, IV fluids): prophylactic medications indicated for ≤24 hours	Prolonged (eg, not rapidly responsive to symptomatic medication and/or brief interruption of infusion); recurrence of symptoms following initial improvement, hospitalization indicated for clinical sequelae (eg, renal impairment, pulmonary infiltrates)	Life-threatening consequences; urgent intervention required	Death
Anaphylaxis	–	–	Symptomatic bronchospasm, with or without urticarial; parenteral intervention indicated; allergy-related edema/angioedema; hypotension	Life-threatening consequences; urgent intervention required	Death
Cytokine release syndrome	Mild reaction; infusion interruption not indicated; intervention not indicated	Therapy or infusion interruption indicated but responds promptly to symptomatic treatment (eg, antihistamines, NSAIDS, narcotics, IV fluids): prophylactic medications indicated for ≤24 hours	Prolonged (eg, not rapidly responsive to symptomatic medication and/or brief interruption of infusion); recurrence of symptoms following initial improvement, hospitalization indicated for clinical sequelae (eg, renal impairment, pulmonary infiltrates)	Life-threatening consequences; pressor or ventilator support indicated	Death

Abstracted from NCI CTCAE Version 4.03.

